## **11.2 Independent Data Safety Monitoring Board**

An independent data safety monitoring board (IDSMB) will review safety data at regular intervals throughout the study. If there are any signs of safety issues, the IDSMB may suggest terminating the trial.

Corresponding to the previously described toxicity pattern for PRRT agents (IAEA PRRT monograph 2013), the IDSMB will put special emphasis on identifying possible acute and delayed radiotoxic effects which are predominantly expected for bone marrow and kidneys.

To identify relevant safety issues in a timely fashion, the IDSMB will perform an ongoing review of SAE notifications, deaths, instances of DMT (see Section 5.4.3.2), instances of patients not meeting the pre-defined eligibility criteria for continued administration of Lu-edotreotide after cycle 1 (see Section 5.4.1.2), or other toxicities requiring discontinuation of Lu-edotreotide treatment in the opinion of the investigator, as well as other AEs of interest (e.g. creatinine values). The IDSMB will prepare summary reports with safety assessments and recommendations. For the first 36 PRRT patients, the IDSMB will review 3 consecutive cohorts of 12 PRRT patients who have reached the day 90 (±14) day evaluation (i.e. baseline for cycle 2), allowing to characterise a representative safety profile at the end of this treatment cycle, but will also consider any available additional data from patients who have already advanced beyond cycle 1 at the time of review. After the first 36 PRRT patients, the IDSMB will convene in 6-monthly intervals. Details will be described in the IDSMB charter.

Results of previous trials have shown that Lu-edotreotide has the potential to perform considerably better than current standard therapy (Baum et al., 2016). Therefore, termination for futility was not considered. Patients who experience progression under everolimus may switch to treatment with Lu-edotreotide off-study at the discretion of the Investigator (see Section 7.4.2).

## **12 Investigator's Obligations and Regulatory Aspects**

### **12.1 Investigator's Commitment**

By signing this protocol, the investigator accepts to carry out all procedures related to this study according to the laws and guidelines of their respective countries related to the conduct of clinical research. All investigators must allow access to all documents pertinent to the study. In particular, the investigator must comply with ICH harmonised tripartite guidelines for Good Clinical Practice

(finalised, July 1996). The investigator's responsibilities as detailed in these guidelines are available upon request.

The study may be subject to inspection or audit by regulatory authorities and will be monitored by authorised company personnel to ensure adherence to these guidelines.

The protocol must be read thoroughly and the instructions herein must be followed exactly. Any deviations should be agreed between the sponsor and the investigator, with appropriate written protocol amendments made to reflect the changes agreed upon. Substantial amendments to the protocol will not be implemented until after approval by the appropriate EC / IRB / regulatory authority according to national legislation (see Section 3.5). Where the deviation occurs for the well-being of the patient, the monitor must be informed and a course of action agreed. Subsequently all such deviations, including the reasons thereof, will be submitted to the sponsor and the IEC(s) / IRB(s) as well as the relevant Competent Regulatory Agencies/Authorities if applicable and according to national regulations.

If an investigator moves, withdraws from the study or retires, the responsibility for conducting the study and maintaining the records may be transferred to another investigator at the same centre who will accept responsibility for taking over the study. Notice of transfer must be made to, and agreed by the sponsor.

## **12.2 Documentation**

### **12.2.1 Approvals and Agreements**

The following documents must be made available to the sponsor prior to enrolling patients into the study:

- Signed final protocol investigator's agreement page.
- Completed and signed investigator agreement, where applicable.
- *Curriculum Vitae* and *Financial disclosure* of the principal investigator together with investigators at his/her centre, where appropriate. Each should be up-to-date, signed and dated, confirming their accuracy.
- Copy of the ethics committee/investigational review board's approval.
- List of members of the ethics committee/investigational review board and their affiliations.
- Sample of the consent form and patient information leaflet to be used (if different from the ones provided by the sponsor).

### **12.2.2 Hospital Case Notes**

The investigator should maintain individual patient records, usually hospital notes. The records should include patient visit dates, records of vital signs, medical history, examinations, any adverse event, and other notes as appropriate. Source documents containing key data relevant to the patient's

condition, procedures and outcome must be kept by the investigator and will be reviewed by the study monitor. All entries in the eCRF must be backed up by source data.

## **13 Ethical and Legal Aspects**

### **13.1 Ethical and Legal Conduct of the Study**

The planning and conduct of this clinical study are subject to national laws. Only when all of the requirements of the appropriate regulatory authority have been fulfilled will the study begin. The guidelines of the World Medical Association Declaration of Helsinki, the Guidelines of GCP (CPMP/ICH/135/95) as well as the demands of national drug and data protection laws and other applicable regulatory requirements will be strictly followed.

The investigator is responsible for ensuring that no patient is subject to any study-related examination or activity before that patient has given informed consent. The patient must give written consent prior to any study-related activity and after the receipt of detailed information. The verbal explanation will cover all the elements specified in the written information provided for the patient.

The investigator will inform the patient of the aims, methods, anticipated benefits and potential hazards of the study including any discomfort it may entail. The investigator will inform patients that in providing informed consent, they are giving permission for representatives of the study centre PIs, ethics committees, or regulatory authorities to inspect their medical records to verify the collected information. Patients will be informed that all personal information made available for inspection will be handled in strictest confidence and in accordance with local data protection laws. The patient must be given every opportunity to clarify any points he/she does not understand and if necessary, ask for more information. At the end of the interview the patient may be given time to reflect if this is required, or if the patient requests more time. Patients will be required to sign and date the informed consent form. After completion, the consent forms will be kept and archived by the investigator in the investigator's study file.

It should be emphasised that the patient has the liberty to withdraw his/her consent to participate at any time, without penalty or loss of benefits to which the patient is otherwise entitled. Patients who refuse to give or withdraw written informed consent may not be included or continued in the study.

### **13.2 Patient Information and Consent**

All relevant information on the study will be summarised in an integrated patient information and consent sheet provided by the sponsor. A sample patient information and informed consent form is provided as a document separate to this protocol.

Based on this patient information sheet, the investigator will explain all relevant aspects of the study to each patient before his/her entry into the study (i.e., before examinations and procedures associated with selection for the study are performed).

The investigator will also mention that written approval of the IRB / IEC has been obtained.

Each patient will have ample time and opportunity to ask questions and will be informed about the right to withdraw from the study at any time without any disadvantage and without having to provide reasons for this decision.

Following this informative discussion, the patient will be asked if he/she is willing to sign and personally date a statement of informed consent, which includes consenting to the processing of his/her data as explained in the patient information sheet. Only if the patient voluntarily agrees to sign the informed consent form and has done so, may he/she enter the study. Additionally, the investigator will personally sign and date the form, too. The patient will receive a duplicate of the signed and dated form.

The signed informed consent statement is to remain in the ISF or, if locally required, in the patient's note / file of the medical institution. In addition, the consent process will be documented in the source documents with an independent entry.

The investigator will document on the CRF the time and date of obtaining informed consent. In the event that informed consent is obtained on the date that baseline study procedures are performed, the study record or patient's clinical record must clearly show that informed consent was obtained prior to these procedures.

If the patient is not capable of providing a signature, a verbal statement of consent can also be given in the presence of an impartial witness (independent of the sponsor and the investigator). This is to be documented by a signature from the informing physician as well as by a signature from the witness. The informed consent form and any other written information provided to patients will be revised whenever important new information becomes available that may be relevant to the subject's consent, or there is an amendment to the protocol which necessitates a change to the content of the patient information and/or the written informed consent form. The investigator will inform the patient of changes in a timely manner and will ask the subject to confirm his/her participation in the study by signing the revised informed consent form. Any revised written informed consent form and written information must receive the IRB / IEC's approval / favourable opinion in advance of use.

### **13.3 Financial Disclosure**

Each investigator (including principal and/or any other investigators; who is directly involved in the treatment or evaluation of research subjects) has to provide a financial disclosure (also on behalf of spouses and dependent children) according to all applicable legal requirements. All relevant documentation will be filed in the TMF and/or ISF, as appropriate.

### **13.4 Publication Policy**

The sponsor is interested in the publication of the results of every study it performs. As some of the information concerning the study drug and the sponsor's development activities may be strictly confidential, any publication manuscript (including conference contributions, etc.) must first be reviewed by the sponsor before its submission or presentation.

Publication of subgroup data and single centre data shall not be performed until the complete study has been published.

All relevant aspects regarding publication will be part of the contract between the sponsor and the investigator / institution.

The sponsor has committed to the global industry position on disclosure of information about clinical trials. The information regarding the study protocol is made publicly available on the internet at [www.clinicaltrials.gov](http://www.clinicaltrials.gov). This derives from the standards that international medical journal editors have established requiring protocol registration at the outset of the study as a prerequisite of consideration for publication.

### **13.5 Compensation for Health Damage of Patients / Insurance**

Where required by the laws and regulations of the country in which the study is performed, insurance of patients against health impairment occurring as a result of participation in the study will be set up in accordance with said laws and regulations. All relevant documentation regarding such insurance will be filed in the TMF and/or ISF, as appropriate.

## Appendix 1: EORTC QLQ-C30

 **EORTC QLQ-C30 (version 3)**

We are interested in some things about you and your health. Please answer all of the questions yourself by circling the number that best applies to you. There are no "right" or "wrong" answers. The information that you provide will remain strictly confidential.

Please fill in your initials: \_\_\_\_\_

Your birthdate (Day, Month, Year): \_\_\_\_\_ 31 \_\_\_\_\_

	Not at All	A Little	Quite a Bit	Very Much
1. Do you have any trouble doing strenuous activities, like carrying a heavy shopping bag or a suitcase?	1	2	3	4
2. Do you have any trouble taking a long walk?	1	2	3	4
3. Do you have any trouble walking or talking outside of the house?	1	2	3	4
4. Do you need to stop walking or a chair during the day?	1	2	3	4
5. Do you need help with cooking, dressing, bathing yourself or using the toilet?	1	2	3	4

**During the past week:**

	Not at All	A Little	Quite a Bit	Very Much
6. Were you limited in doing either your work or other daily activities?	1	2	3	4
7. Were you limited in pursuing your hobbies or other leisure time activities?	1	2	3	4
8. Were you short of breath?	1	2	3	4
9. Have you had pain?	1	2	3	4
10. Did you need to rest?	1	2	3	4
11. Have you had trouble sleeping?	1	2	3	4
12. Have you felt weak?	1	2	3	4
13. Have you lacked appetite?	1	2	3	4
14. Have you felt nauseated?	1	2	3	4
15. Have you vomited?	1	2	3	4
16. Have you been constipated?	1	2	3	4

Please go on to the next page

**During the past week:**

	Not at All	A Little	Quite a Bit	Very Much
17. Have you had diarrhea?	1	2	3	4
18. Were you tired?	1	2	3	4
19. Did pain interfere with your daily activities?	1	2	3	4
20. Have you had difficulty in concentrating on things, like reading a newspaper or watching television?	1	2	3	4
21. Did you feel tense?	1	2	3	4
22. Did you worry?	1	2	3	4
23. Did you feel nervous?	1	2	3	4
24. Did you feel depressed?	1	2	3	4
25. Have you had difficulty remembering things?	1	2	3	4
26. Has your physical condition or medical treatment interfered with your family life?	1	2	3	4
27. Has your physical condition or medical treatment interfered with your social activities?	1	2	3	4
28. Has your physical condition or medical treatment caused you financial difficulties?	1	2	3	4

**For the following questions please circle a number between 1 and 7 that best applies to you**

	1	2	3	4	5	6	7
29. How would you rate your overall health during the past week?	1	2	3	4	5	6	7
Very poor							Excellent
30. How would you rate your overall quality of life during the past week?	1	2	3	4	5	6	7
Very poor							Excellent

© Copyright 1993 EORTC Quality of Life Group. All rights reserved. Version 3.0

## Appendix 2: EORTC QLQ-GI.NET21

ENGLISH

EORTC QLQ – GI.NET21

Patients sometimes report that they have the following symptoms or problems. Please indicate the extent to which you have experienced these symptoms or problems during the past week. Please answer by circling the number that best applies to you.

During the past week:		Not at all	A little	Quite a bit	Very much	
31.	Did you have hot flushes?	1	2	3	4	
32.	Have you noticed or been told by others that you looked flushed/red?	1	2	3	4	
33.	Did you have night sweats?	1	2	3	4	
34.	Did you have abdominal discomfort?	1	2	3	4	
35.	Did you have a bloated feeling in your abdomen?	1	2	3	4	
36.	Have you had a problem with passing wind/gas/flatulence?		2	3	4	
37.	Have you had acid indigestion or heartburn?	1	2	3	4	
38.	Have you had difficulties with eating?	1	2	3	4	
39.	Have you had side-effects from your treatment? (If you are not on treatment please circle N/A)	N/A	1	2	3	4
40.	Have you had a problem from repeated injections? (If not having injections please circle N/A)	N/A	1	2	3	4
41.	Were you worried about the tumour occurring in other areas of the body?	1	2	3	4	
42.	Were you concerned about disruption of home life?	1	2	3	4	
43.	Have you worried about your health in the future?	1	2	3	4	
44.	How distressing has your illness or treatment been to those close to you?	1	2	3	4	
45.	Has weight loss been a problem for you?	1	2	3	4	
46.	Has weight gain been a problem for you?	1	2	3	4	
47.	How worried about the results of your tests? (If you have not had tests please circle N/A)	N/A	1	2	3	4
48.	Have you had aches or pains in your muscles or bones?	1	2	3	4	
49.	Did you have any limitations in your ability to travel?	1	2	3	4	
During the past four weeks:						
50.	Have you had problems receiving adequate information about your disease and treatment?	1	2	3	4	
51.	Has the disease or treatment affected your sex life (for the worse)? (If not applicable please circle N/A)	N/A	1	2	3	4

### Appendix 3: Karnofsky Performance Status (KPS) Scale

The performance status is an attempt to quantify cancer patients' general well-being and activities of daily life. This study uses the performance status scale according to Karnofsky and Burchenal, 1949.

[Table 8](#) shows definition of scales in relation to ECOG score.

**Table 8: Karnofsky Performance Status (KPS) Scale**

KPS scale [%]	ECOG score	Definition
100	0	Normal; no complaints; no evidence of disease.
90	0	Able to carry on normal activity; minor signs or symptoms of disease.
80	1	Normal activity with effort; some signs or symptoms of disease.
70	1	Cares for self; unable to carry on normal activity or to do active work.
60	2	Requires occasional assistance, but is able to care for most of his personal needs.
50	2	Requires considerable assistance and frequent medical care.
40	3	Disabled; requires special care and assistance.
30	3	Severely disabled; hospital admission is indicated although death not imminent.
20	4	Very sick; hospital admission necessary; active supportive treatment necessary.
10	4	Moribund; fatal processes progressing rapidly.
0	5	Dead

## Appendix 4: Afinitor Dose Adjustment Recommendations

(see Afinitor®, current version of local product information for the countries participating in this study)

**Table 9: Afinitor Dose Adjustment Recommendations**

Adverse reaction	Severity 	Afinitor dose adjustment
Non-infectious pneumonitis	Grade 2	Consider interruption of therapy until symptoms improve to Grade ≤1. Re-initiate treatment at 5 mg daily. Discontinue treatment if failure to recover within 4 weeks.
	Grade 3	Interrupt treatment until symptoms resolve to Grade ≤1. Consider re-initiating treatment at 5 mg daily. If toxicity recurs at Grade 3, consider discontinuation.
	Grade 4	Discontinue treatment.
Stomatitis	Grade 2	Temporary dose interruption until recovery to Grade ≤1. Re-initiate treatment at same dose. If stomatitis recurs at Grade 2, interrupt dose until recovery to Grade ≤1. Re-initiate treatment at 5 mg daily.
	Grade 3	Temporary dose interruption until recovery to Grade ≤1. Re-initiate treatment at 5 mg daily.
	Grade 4	Discontinue treatment.
Other non-haematological toxicities (excluding metabolic events)	Grade 2	If toxicity is tolerable, no dose adjustment required. If toxicity becomes intolerable, temporary dose interruption until recovery to Grade ≤1. Re-initiate treatment at same dose. If toxicity recurs at Grade 2, interrupt treatment until recovery to Grade ≤1. Re-initiate treatment at 5 mg daily.
	Grade 3	Temporary dose interruption until recovery to Grade ≤1. Consider re-initiating treatment at 5 mg daily. If toxicity recurs at Grade 3, consider discontinuation.
	Grade 4	Discontinue treatment.
Metabolic events (e.g. hyperglycaemia, dyslipidaemia)	Grade 2	No dose adjustment required.
	Grade 3	Temporary dose interruption. Re-initiate treatment at 5 mg daily.
	Grade 4	Discontinue treatment.
Thrombocytopenia	Grade 2 ( $<75, \geq 50 \times 10^9/l$ )	Temporary dose interruption until recovery to Grade ≤1 ( $\geq 75 \times 10^9/l$ ). Re-initiate treatment at same dose.
	Grade 3 & 4 ( $<50 \times 10^9/l$ )	Temporary dose interruption until recovery to Grade ≤1 ( $\geq 75 \times 10^9/l$ ). Re-initiate treatment at 5 mg daily.
Neutropenia	Grade 2 ( $\geq 1 \times 10^9/l$ )	No dose adjustment required.
	Grade 3 ( $<1, \geq 0.5 \times 10^9/l$ )	Temporary dose interruption until recovery to Grade ≤2 ( $\geq 1 \times 10^9/l$ ). Re-initiate treatment at same dose.
	Grade 4 ( $<0.5 \times 10^9/l$ )	Temporary dose interruption until recovery to Grade ≤2 ( $\geq 1 \times 10^9/l$ ). Re-initiate treatment at 5 mg daily.
Febrile neutropenia	Grade 3	Temporary dose interruption until recovery to Grade ≤2 ( $\geq 1.25 \times 10^9/l$ ) and no fever. Re-initiate treatment at 5 mg daily.
	Grade 4	Discontinue treatment.
1 Grading based on National Cancer Institute (NCI) Common Terminology Criteria for Adverse Events (CTCAE) v4.03		

Special populations:

Elderly patients ( $\geq 65$  years)

- No dose adjustment is required (see Section 5.2 of the original document),

Renal impairment

- No dose adjustment is required (See Section 5.2 of the original document)

Hepatic impairment

- Mild hepatic impairment (Child-Pugh A) – the recommended dose is 7.5 mg daily.
- Moderate hepatic impairment (Child-Pugh B) – the recommended dose is 5 mg daily.
- Severe hepatic impairment (Child-Pugh C) – Afinitor is only recommended if the desired benefit outweighs the risk. In this case, a dose of 2.5 mg daily must not be exceeded.

Dose adjustments should be made if a patient's hepatic (Child-Pugh) status changes during treatment (see also Sections 4.4 and 5.2 of the original document).

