### 5.1.4 Pharmaceutical Properties of Everolimus (Afinitor®)

Everolimus has been licensed for the treatment of several types of cancer including progressive neuroendocrine tumours of pancreatic origin (P-NET) and non-functional gastroenteric origin (GE-NET) with unresectable, locally advanced or metastatic disease.

Afinitor® tablets are supplied for oral administration and contain 10 mg of everolimus. For patients not tolerating the regular dose of 10 mg, tablets containing 5 mg will also be available, to be administered according to the manufacturer's instructions for dose reduction. The tablets also contain anhydrous lactose, butylated hydroxytoluene, crospovidone, hypromellose, lactose monohydrate, and magnesium stearate as inactive ingredients. The tablets are white to slightly yellow, elongated with a bevelled edge and no score, and engraved with "UHE" on one side and "NVR" on the other.

Everolimus will be purchased from licensed commercial sources, and labelled by the central pharmacy, according to the requirements of the participating countries. Details will be described in the separate document Investigational Medicinal Product (IMP)-Management Plan.

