### **5.5.2 Everolimus (Afinitor®)**

Commercial drug product will be purchased from the manufacturer (Novartis Pharma Stein AG; Stein, Switzerland) or a licensed pharmaceutical wholesaler, able to provide lot documentation and will be labelled according to the requirements as described above.

Tablets will be available with the following strengths: 10 mg and 5 mg.

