### 8.3.5 Clinical Laboratory Tests

Blood and urine samples for clinical laboratory parameters will be collected for all subjects at the points of time given in [Table 1](#) and [Table 2](#).

Laboratory assessments will be performed by the institutional or local laboratories. Because of the potential for radioactivity in some blood and urine samples, the local laboratory must adhere to their SOPs and/or any guidance and regulations for handling radioactive substances.

Lu-edotreotide arm ONLY: at study site wherever possible. If not logistically feasible, inter-visit lab samples can be taken by a medical general practitioner (GP) in the vicinity of the patient's home.

Samples will be tested for the following parameters:

Haematology: haemoglobin, haematocrit, mean corpuscular volume (MCV), mean corpuscular haemoglobin (MCH), white blood cell count (total and differential: leukocytes, neutrophils, eosinophils, basophils, lymphocytes, monocytes), red blood cells, platelets.

Biochemistry: sodium, potassium, chloride, calcium, glucose, creatinine, urea, albumin, total bilirubin, aspartate transaminase (AST), alanine transaminase (ALT), alkaline phosphatase (AP), gamma-glutamyl transferase (GGT), lipase, amylase, total protein.

Clotting parameters: prothrombin time (quick), reagent-independent prothrombin ratio (international normalised ratio; INR), activated partial thromboplastin time (aPTT).

Urinalysis (dipstick accepted): specific gravity, pH, protein, glucose, blood, leukocytes, ketones, nitrite, albumin, creatinine. Alpha-1-microglobulin will also be tested in urine but only in centres with adequate technical equipment and an established test method.

Tumour marker: Chromogranin-A, further markers (see Section [8.2.1.3](#)).

The investigator will sign each laboratory printout and assess clinical significance. Clinically significant values have to be highlighted as "c.s." (clinically significant). The printouts will be included in the patient's file.

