8.4 Clinical Laboratory Evaluations

Haematology: haemoglobin, haematocrit, mean corpuscular volume (MCV), mean corpuscular haemoglobin (MCH), white blood cell count (total and differential: leukocytes, neutrophils, eosinophils, basophils, lymphocytes, monocytes), red blood cells, platelets.

Biochemistry: sodium, potassium, chloride, calcium, glucose, creatinine, urea, albumin, total bilirubin, aspartate transaminase (AST), alanine transaminase (ALT), alkaline phosphatase (AP), gamma-glutamyl transferase (GGT), lipase, amylase, total protein,.

Clotting parameters: prothrombin time (quick), reagent-independent prothrombin ratio (international normalised ratio; INR), activated partial thromboplastin time (aPTT).

Urinalysis: specific gravity, pH, protein, glucose, blood, leukocytes, ketones, nitrite, albumin, creatinine; α -1-microglobulin will also be tested in urine but only in centres with adequate technical equipment and an established test method.

Tumour markers: Chromogranin-A, further markers

All lab parameters will be summarised by visit and treatment arms as continuous data (raw and change from baseline) or category data where appropriate (e.g. urine test with category units).

The following parameters will also be presented as boxplot graphs by visit and treatment arm: WBC, RBC, HB, Neutrophils, Lymphocytes, Platelets, alkaline phosphatase, bilirubin, AST, ALT, albumin, potassium, sodium, calcium, and tumour markers.

For the following parameters the percentage of patients experiencing CTCAE toxicity will also be summarised by worst CTCAE grades (all grades pooled and Grades 3 and 4 pooled) and by treatment arm for baseline and post first IMP dosing parts of the study:

ITM-LET-01	Statistical Analysis Plan
------------	---------------------------

Table 6: List of laboratory parameters to be analysed according to CTCAE guidelines

Lab parameter	CTCAE term:
Lymphocytes	Lymphocyte count increased
	Lymphocyte count decreased
Hb	Anaemia
Leukocytes	Leukocytosis
	White blood cell decreased
Platelets	Platelet count decreased
PNN	Neutrophil count decreased
Creatinine	Creatinine increased
Fasting blood glucose	Hypoglycaemia
	Hyperglycaemia
Calcium	Hypocalcaemia
	Hypercalcaemia
Potassium	Hypokalaemia
	Hyperkalaemia
Sodium	Hyponatremia
	Hypernatremia
GGT	GGT increased
Alkaline Phosphatase	Alkaline Phosphatase increased
AST	AST increased
ALT	ALT increased
Total bilirubin	Blood bilirubin increased
Albumin	Hypoalbuminemia

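### Parts of the everolimus dose-adjustment appendix do not match the tablets supplied or the laboratory panel, and the SAP grades glucose as fasting although the protocol sets no fasting condition

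*Protocol*

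**What the plan says.** Protocol 5.4.2 and 5.4.3.1, and footnote S to the everolimus flow chart (Table 2), refer everolimus dose reductions to Appendix 4.

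- **Hepatic doses.** Below Table 9, for Child-Pugh A "the recommended dose is 7.5 mg daily". For B the figure is 5 mg daily. For C the drug is advised only where benefit outweighs risk, and then "a dose of 2.5 mg daily must not be exceeded". The dose is to be adjusted if the class changes on treatment.
- **Tablets.** Protocol 5.5.2 says: "Tablets will be available with the following strengths: 10 mg and 5 mg". Protocol 5.1.4 describes them as "elongated with a bevelled edge and no score", and 5.4.2 has them taken whole, once a day. Both 5.4.2 and the Day 0 visit (7.3.1.1) start patients on 10 mg, with no hepatic exception.
- **Metabolic events.** Table 9 has a row group for "Metabolic events (e.g. hyperglycaemia, dyslipidaemia". At Grade 3 the action is "Temporary dose interruption. Re-initiate treatment at 5 mg daily"; at Grade 4 treatment is discontinued.
- **Laboratory panel.** The biochemistry list in 8.3.5 opens with the electrolytes, includes glucose without a sampling condition, and ends with "gamma-glutamyl transferase (GGT), lipase, amylase, total protein". SAP 8.4 repeats the list.
- **Glucose grading.** SAP Table 6 names "Fasting blood glucose" as the parameter for hypo- and hyperglycaemia. Results are summarised by worst CTCAE grade and by arm.

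**The concern.** A dosing appendix should be workable from what the protocol dispenses and measures. Where it is not, each site must improvise, and sites may do so differently. Here a stated daily dose has no tablet behind it, and the class that triggers it is not recorded. A trigger that interrupts or ends treatment has no scheduled laboratory value.

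The glucose point is separate. It does not stop anyone following Appendix 4. It concerns whether the SAP's graded laboratory table describes the samples that are taken. Protocol 1.3 names hyperglycaemia among the side effects of everolimus, so this is a safety comparison that readers will look for.

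**Working it through.** **1. Which daily doses can be dispensed.** With whole tablets, the daily dose is 5a + 10b mg, where a and b are whole numbers. This gives 5 mg (one 5 mg tablet) and 10 mg (one 10 mg or two 5 mg). It cannot give 7.5 mg, which needs half a 5 mg tablet, or 2.5 mg, which is half the smallest tablet. Of the three hepatic lines (7.5, 5 and at most 2.5 mg daily), only the 5 mg line can be dispensed as stated. Child-Pugh class appears only in Appendix 4. It is not in the baseline data (8.1), the visit descriptions (section 7) or the SAP.

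**2. How much of Table 9 is affected.** Grade rows: pneumonitis 3, stomatitis 3, other non-haematological 3, metabolic 3, thrombocytopenia 2, neutropenia 3, febrile neutropenia 2. The total is 19. Every action in them is no change, interruption, the same dose, 5 mg or discontinuation, so none needs another tablet strength. Only the 3 metabolic rows involve lipids, and only for their dyslipidaemia part, because glucose is measured. The other 19 − 3 = 16 rows are unaffected by this point.

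**3. Lipids in the panel.** Protocol 8.3.5 lists 16 biochemistry analytes. None is cholesterol, triglycerides or another lipid; lipase is an enzyme. SAP Table 6 has no lipid row.

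**4. Glucose samples by arm.** No visit description or flow-chart footnote requires fasting, and 5.4.2 allows everolimus to be taken consistently with food. The number of scheduled chemistry draws also differs:

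- Everolimus, months 0–11: one per monthly visit, so 12.
- PRRT, months 0–11: the same 12, plus draws at 5 h and 24 h after each of up to four infusions (7.3.1.1, 7.3.1.2, 7.3.3.1, 7.3.3.2): 12 + 2 × 4 = 20. This reproduces the 20 biochemistry samples in Protocol Table 7, against 12 for clotting parameters.
- After the first dose, leaving out the Day 0 pre-dose draw: 20 − 1 = 19 against 12 − 1 = 11.

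This assumes all four cycles are given, all visits are attended, and the post-infusion serum chemistry includes glucose as in the 8.3.5 list. A worst-grade summary takes the maximum over all draws, so it depends on how many there are. Here the number differs by arm and fasting status is unknown in both.

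**5. Exposure, for illustration only.** If PFS on everolimus is exponential with median 11 months and treatment runs to progression or month 30, mean time on drug is (1 − exp(−30 ln 2/11))/(ln 2/11) = 13.5 months. For 100 patients that is about 1,350 patient-months without a scheduled lipid value. It ignores earlier stopping for toxicity and dropout.

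**The case against.** The strongest reply is that most of the appendix works, and that is correct. A reader might infer that Appendix 4 as a whole cannot be carried out. The documents do not support that: 16 of 19 grade rows and the 5 mg hepatic line can be followed. The 2.5 mg figure is a ceiling under a benefit-risk condition, so withholding the drug would comply. The firm supply conflict is therefore the 7.5 mg line.

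The number of patients concerned is also open. Entry excludes clinically relevant hepatic dysfunction (Protocol 4.2.2, criterion 19). The documents contain no Child-Pugh scoring, so they do not show how many would fall under the hepatic lines. They do not exclude such patients either: liver tumour burden up to 70% is allowed, as is albumin below 3 g/dL with a normal prothrombin time, and the class may change on treatment. Supply details are deferred to an IMP management plan that is not among the documents, but 5.5.2 states the strengths outright.

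On lipids, a reader might infer that dyslipidaemia can never be observed. That goes too far. Appendix 4 points to the local product information, section 8 allows extra visits at any time, and 8.3.2.3 requires clinically relevant abnormal results to be recorded as adverse events. What stands is that detection depends on ad hoc local testing.

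On glucose, a reader might infer that the metabolic comparison is wrong in a known direction. No misgrading is shown in size or direction. The SAP label could mean that only fasting values are graded, but nothing collected would identify those values. Hyperglycaemia is also reported as an investigator-graded adverse event, and glucose is summarised by visit and arm, so Table 6 is not the only source.

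**Conclusion.** The point holds in limited form, as three mismatches that should be corrected:

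- Two of the three hepatic lines in Appendix 4 name doses that cannot be made from the supplied tablets, one of them only a conditional ceiling. The class that triggers them is not recorded.
- The Grade 3 and Grade 4 metabolic actions name dyslipidaemia, for which no measurement is scheduled.
- SAP Table 6 grades a fasting quantity that the protocol does not collect as such. With up to 19 against 11 post-dose chemistry draws in months 0–11, the worst-grade glucose comparison between arms is unreliable.

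The first two follow from setting the passages side by side and need no numerical assumption. The draw counts in the third rest on the assumptions in the working. The primary and key secondary endpoints, the type I error and the power are not affected. The 1,350 patient-months measure exposure, not harm; the documents give no frequency of dyslipidaemia or hepatic impairment from which harm could be estimated.

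**What to change.** - **Hepatic doses.** Reconcile the hepatic part of Appendix 4 with Protocol 5.1.4, 5.4.2, 5.5.2 and 7.3.1.1. Which doses and supply apply is for the sponsor to settle; either side could be amended. Record in the CRF whatever inputs the retained hepatic rule needs.
- **Lipids.** Reconcile Table 9 with the panel in 8.3.5 so that any retained lipid trigger has a scheduled measurement, for example lipid analytes on the serum chemistry already drawn. Add a matching row to SAP Table 6.
- **Glucose.** Record fasting status with each glucose value and apply fasting-based grades only to samples recorded as fasting. Otherwise relabel the SAP row to match what is collected, which is the only option for samples whose fasting status was not noted.

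The cost is a few extra assays on an existing tube, one or two CRF fields, a wording or supply correction, and an edit to one SAP table.
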